13.1. Definitions and Classifications

Adverse Event (AE) – An AE is “any untoward medical occurrence, unintended disease or injury, or untoward clinical signs (including abnormal laboratory findings) in subjects, users or other persons, whether or not related to the investigational medical device.

NOTES:

Note 1 to entry: This definition includes events related to the investigational medical device or the comparator.

Note 2 to entry: This definition includes events related to the procedures involved.

Note 3 to entry: For users or other persons, this definition is restricted to events related to investigational medical devices.”¹

In this study, monitored AEs will be confined to ocular AEs or non-ocular AEs related to the study lenses (e.g. injury sustained through poor vision).

Serious Adverse Event (SAE) – An SAE is any untoward medical occurrence that:

- Is potentially sight-threatening
- Requires in-patient hospitalization or prolongation of existing hospitalization
- Results in persistent or significant disability/incapacity (e.g., a sight threatening event, a significant persistent or permanent change, impairment, damage, or disruption to the subject’s body)
- Requires intervention to prevent permanent damage (the use of the test article resulting in a condition which requires medical or surgical intervention to preclude permanent impairment of the body structure or a body function). Important medical events that may not result in death, be life-threatening, or require hospitalization may be considered an SAE when, based upon appropriate medical judgment, they may jeopardize the patient or subject and may require medical or surgical intervention to prevent one of the outcomes listed in the above definition

Diagnoses and conditions that are considered Ocular Serious Adverse Events include, but not limited to:

- Microbial Keratitis (MK)
- Iritis (including cells in the anterior chamber)
- Permanent decrease in best spectacle corrected visual acuity equivalent to 2 acuity lines or greater
- Central Corneal Opacity
- Central Corneal Neovascularization
- Uveitis
- Endophthalmitis
- Hypopyon

- Hyphema
- Penetration of Bowman's Membrane
- Persistent Epithelial Defect
- Limbal cell Damage

Significant Adverse Events – Those events that are usually symptomatic and warrant discontinuation (temporary or permanent) of the test article (excluding Serious Adverse Events).

Diagnoses and conditions that are considered Ocular Significant Adverse Events include, but not limited to the following:

- Contact Lens Induced Peripheral Ulcer (CLPU)
- Significant Infiltrative Events (SIE)
- Superior Epithelial Arcuate Lesions (SEALs)
- Any Temporary Loss of >2 Lines of BSCVA
- Other grade 3 or higher corneal findings, such as abrasions or edema
- Non-contact lens related corneal events - e.g. Epidemic Keratoconjunctivitis (EKC)
- Asymptomatic Corneal Scar
- Any corneal event which necessitates temporary lens discontinuation > 2 weeks

Non-Significant Adverse Events – Those conditions that are usually asymptomatic and usually do not warrant discontinuation (temporary or permanent) of the test article. However, the Investigator may choose to treat as a precautionary measure.

Diagnoses and conditions that are considered Ocular Non-Significant Adverse Events include, but not limited to the following:

- Non-significant Infiltrative Event (NSIE)
- Contact Lens Papillary Conjunctivitis (CLPC)
- Superficial Punctate Keratitis (SPK)
- Conjunctivitis: Bacterial, Viral, Allergic
- Blepharitis
- Meibomianitis
- Contact Dermatitis
- Localized Allergic Reactions
- Any corneal event not explicitly defined as serious or significant adverse event, which necessitates temporary lens discontinuation < 2 weeks

Adverse Device Effect (ADE) – An ADE is an “adverse event related to the use of an investigational medical device.

NOTES:

Note 1 to entry: This definition includes adverse events resulting from insufficient or inadequate instructions for use, deployment, implantation, installation, or operation, or any malfunction of the investigational medical device.

Note 2 to entry: This definition includes any event resulting from use error or from intentional misuse of the investigational medical device.”¹

Unanticipated Serious Adverse Device Effect (USADE) – Any serious adverse effect on health or safety or any life-threatening problem or death caused by, or associated with, the test

article, if that effect, problem, or death was not previously identified in nature, severity, or degree of incidence in the investigational plan, Investigator's Brochure or protocol, or any other unanticipated serious problem associated with the test article that relates to the rights, safety and welfare of subjects.

13.2. Assessing Adverse Events

In conjunction with the medical monitor, the Investigator will evaluate adverse events to ensure the events are categorized correctly. Elements of categorization will include:

- Seriousness/Classifications (see definition in Section 13.1)
- Causality or Relatedness – i.e. the relationship between the test article, study treatment or study procedures and the adverse event (not related; unlikely related; possibly related; related - see definition in Section 13.2.1)
- Adverse Event Severity – Adverse event severity is used to assess the degree of intensity of the adverse event (mild; moderate; severe for all events - see definition in Section 13.2.2)
- Outcome – not recovered or not resolved; recovering or resolving; recovered or resolved with sequelae; recovered or resolved; death related to adverse event; unknown
- Actions Taken – none; temporarily discontinued; permanently discontinued; other.

13.2.1. Causality Assessment

Causality Assessment – A determination of the relationship between an adverse event and the test article. The test article relationship for each adverse event should be determined by the investigator using these explanations:

- Not Related- An adverse event that is not related to the use of the test article, study treatment or study procedures
- Unlikely Related – An adverse event for which an alternative explanation is more likely, e.g. concomitant treatment, concomitant disease(s), or the relationship of time suggests that a causal relationship is not likely
- Possibly Related – An adverse event that might be due to the use of the test article, or to the study treatment or study procedures. An alternative explanation, e.g. concomitant treatment, concomitant disease(s), is inconclusive. The relationship in time is reasonable. Therefore, the causal relationship cannot be excluded
- Related – An adverse event that is listed as a possible adverse effect (device) or adverse reaction (drug) and cannot be reasonably explained by an alternative explanation, e.g. concomitant treatment of concomitant disease(s). The relationship in time is very suggestive, e.g. it is confirmed by de-challenge and re-challenge.

13.2.2. Severity Assessment

Severity Assessment – A qualitative assessment of the degree of intensity of an adverse event as determined by the Investigator or reported to him/her by the subject. The assessment of severity is made irrespective of test article, study treatment or study procedure relationship or seriousness of the event and should be evaluated according to the following scale:

- Mild – Event is noticeable to the subject, but is easily tolerated and does not interfere with the subject's daily activities

- Moderate – Event is bothersome, possible requiring additional therapy, and may interfere with the subject's daily activities
- Severe – Event is intolerable, necessitates additional therapy or alteration of therapy and interferes with the subject's daily activities.

13.3. Documentation and Follow-Up of Adverse Events

If a subject reports through the follow-up questionnaire 'a problem with their eyes while wearing lenses that required them to visit an eyecare practitioner or hospital', this will be followed-up with the treating facility. If this is the ECP investigator, they will be asked to complete a paper adverse event form and to supply copies of any other relevant records. In the event of the subject having been seen by another clinic (e.g. emergency room) copies of the medical records will be requested.

Investigators are recommended to include the following in the patients records:

- Adverse event (diagnosis not symptom)
- Drawings or photographs (where appropriate) that detail the finding (e.g., size, location, and depth, etc.)
- Date the clinical site was notified
- Date and time of onset
- Date and time of resolution
- Adverse event classification, severity, and relationship to test articles, as applicable
- Treatment regimen instituted, including concomitant medications prescribed, in accordance with applicable licensing requirements
- Any referral to another health care provider if needed
- Outcome, ocular damage (if any)
- Likely etiology
- Best corrected visual acuity at the discovery of the event and upon conclusion of the event.

13.4. Reporting Adverse Events

In addition, a written report will be submitted by the Principal Investigator to the IEC/IRB according to their requirements. The report will comment whether the adverse event was considered to be related to the test article, study treatment or study procedures.

13.5. Event of Special Interest

None

13.6. Reporting of Pregnancy

Not applicable for this study.

14. STATISTICAL METHODS

14.1. General Considerations

Statistical Analysis will be undertaken by the sponsor or under the authority of the sponsor. A general description of the statistical methods to be implemented in this clinical trial is outlined below. More details will be included in the stand-alone Statistical Analysis Plan (SAP). The SAP will be finalized prior to database lock.

All data summaries and statistical analyses will be performed using the SAS software 9.4 or higher (SAS Institute, Cary, NC).⁷ Throughout the analysis of data, the results for each subject/eye will be used when available for summarization and statistical analysis.

Summary tables (descriptive statistics and/or frequency tables) will be provided by arm for all baseline variables, ECP registration questionnaire (ERQ), Patient registration questionnaire (PRQ), and 2-week, 4-month and 12-month survey questionnaires. Continuous variables will be summarized with descriptive statistics (n, mean, standard deviation (SD), median, minimum and maximum). Frequency count and percentage of subjects or eyes within each category will be provided for categorical data.

The plan is to enroll 300 subjects per arm with a target completion of 240 subjects per arm. During the enrollment period, the subject's dropouts will be monitored. If the dropout rate is over 20% in certain arms, the targeted total enrollment number will be increased accordingly to ensure a minimum of 240 subjects per group to complete the study.

14.3. Analysis Populations

Per-Protocol Population:

All eligible subjects who have completed at least two follow-up questionnaires including the 12-month questionnaire and did not substantially deviate from the protocol as determined by the trial cohort review committee prior to database hard lock (Per-Protocol Population). Justification of excluding subjects with protocol deviations in the per-protocol population set will be documented in a memo to file.

Full Analysis Population:

All enrolled subjects (signed consent form) regardless of subsequent withdrawal from study or deviation from protocol. At least one observation should be recorded.

Both primary and secondary analysis will be conducted on full analysis set. A sensitivity analysis will be conducted on the per-protocol population. To evaluate the impact of missing data, sensitivity analysis will be conducted using multiple imputation.

14.4. Level of Statistical Significance

All planned analysis for this study will be conducted with an overall type I error rate of 5%. The secondary analysis will be adjusted for multiple comparisons between the Test and the Control groups across the evaluation periods using a simulated-based approach (Edward and Berry).¹⁵

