2.3. Hypotheses

Primary Hypotheses

Subjects wearing JJVC senofilcon A contact lenses with photochromic additive (ACUVUE® OASYS with Transitions™ contact lenses) will have superior vision satisfaction in bright lighting compared to subjects wearing non-photochromic reusable silicone hydrogel contact lenses over a period of one year.

Secondary Hypotheses

1. Subjects wearing JJVC senofilcon A contact lenses with photochromic additive (ACUVUE® OASYS with Transitions™ contact lenses) will have superior vision satisfaction compared to subjects wearing non-photochromic reusable silicone hydrogel contact lenses at 12-month evaluation. This hypothesis will also be tested at 2-week and 4-month evaluation periods.
2. Subjects wearing JJVC senofilcon A contact lenses with photochromic additive (ACUVUE® OASYS with Transitions™ contact lenses) will have superior overall quality of vision compared to subjects wearing non-photochromic reusable silicone hydrogel contact lenses over a period of one year. This hypothesis will also be tested at each evaluation period.
3. Subjects wearing JJVC senofilcon A contact lenses with photochromic additive (ACUVUE® OASYS with Transitions™ contact lenses) will have superior overall comfort compared to subjects wearing non-photochromic reusable silicone hydrogel contact lenses over a period of one year. This hypothesis will also be tested at each evaluation period.

No hypotheses are formulated about Pulfrich effect or, serious and significant ocular adverse events (AEs). The following will be calculated by arm:

1. Proportion of subjects who experienced the Pulfrich effect at each evaluation period.
2. Incidence rate of serious and significant ocular AEs (in patient-year)

3. Proportion of subjects with at least one reported serious or significant ocular AE at each evaluation period.
4. Proportion of eyes with at least one reported serious or significant ocular AE at each evaluation period.
5. Proportion of all reported serious and significant ocular AEs at each evaluation period.

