14.5. Primary Analysis

Vision Satisfaction in Bright Lighting

Subjects' responses will first be categorized into a binary outcome of 1 if the response is positive (Agree or Strongly Agree) or 0 otherwise (Neither Agree Nor Disagree, Disagree or Strongly Disagree). The outcome will then be analyzed using a generalized linear mixed model for correlated binary data. The model will include treatment group (Test, Control), evaluation period (2-week, 4-month and 12-month) and group by evaluation period as fixed factors, and site as random effect (G-side). The model will be adjusted for baseline values, country, age, gender and race as fixed covariates when appropriate. The correlation between responses from the same subjects across evaluation periods will be modeled using an unstructured (UN) covariance matrix (R-side). If problem of convergence encountered, a Compound Symmetry (CS) covariance structure will be considered.

The null and alternative hypotheses for the primary hypothesis are as follows:

$$\begin{aligned} H_0: OR &\leq 1 \\ H_A: OR &> 1; \end{aligned}$$

where OR is the overall odds ratio of having a positive rating of vision satisfaction in bright lighting (Test over Control). The superiority test will be based on the OR and corresponding 95% confidence interval calculated using the final selected model. The lower bound of the 95% confidence interval will be compared to 1. If the lower bound is above 1, the Test lens will be considered superior to the Control lenses with respect to vision satisfaction in bright lighting. The odds ratio at 2-week, 4-month and 12-month evaluation periods will be calculated with their corresponding adjusted 95% confidence intervals to test the secondary hypothesis #1.

This is an observational study and the treatment assignment is not randomized. The Test and Control groups may have large differences on their baseline characteristics, and these differences can lead to biased estimates of treatment effects. Instead of adjusting the model to all covariates including interactions with treatment group and higher order terms, the propensity score will be used. The propensity score, defined as the conditional probability of

being in Test or Control group given the covariates, will be used to balance the covariates in the two groups, and therefore reduce this bias. The propensity will be calculated using a logistic regression model.

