14.6. Secondary Analysis

Overall Quality of Vision and Overall Comfort

Overall quality of vision and overall comfort ratings will be analyzed separately using the same statistical method described in the primary analysis. The hypothesis tests will be conducted using adjusted 95% confidence intervals of odds ratios.

Pulfrich Effect

The proportion of subjects who experienced the Pulfrich effect will be calculated as the proportion of subjects who disagree or strongly disagree with the statement “While wearing these lenses, my depth perception of moving objects has NOT been impacted”. The Pulfrich effect will be evaluated over time at 2-week, 4-month and 12-month evaluation periods. The proportion of subjects who experienced the Pulfrich effect at least once will also be calculated.

Serious and Significant Ocular AEs

No statistical hypothesis will be tested. The following will be calculated:

1. Incidence rate of serious and significant ocular AEs (in patient-year) will be calculated as follow:

$$IR = \frac{\text{Number of subjects with an event}}{(\text{Sum of subjects' exposure times})/365.25}$$

Where each subject's exposure time is defined as number of days in the study after the enrollment, censored only by events such as first serious or significant ocular AE, dropouts, death or the end of the study.

2. Proportion of subjects with at least one reported serious or significant ocular AE at each evaluation period.
3. Proportion of eyes with at least one reported serious or significant ocular AE at each evaluation period.
4. Proportion of all reported serious and significant ocular AEs at each evaluation period.

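### Section 14.4 promises an overall 5% type I error for all planned analysis, but the only stated control is across evaluation periods, not across the three superiority endpoints

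*Combined protocol and SAP*

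**What the plan says.** Section 14.4 makes two statements. The first is the promise: "All planned analysis for this study will be conducted with an overall type I error rate of 5"%. The second is the control: "The secondary analysis will be adjusted for multiple comparisons between the Test and the Control groups across the evaluation periods", by a simulation-based method.

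Section 2.3 states superiority hypotheses on three endpoints. Bright-light satisfaction over one year is the primary hypothesis, and its results by period form secondary hypothesis 1. Overall quality of vision (hypothesis 2) and overall comfort (hypothesis 3) are each tested over one year, and for each the section adds: "This hypothesis will also be tested at each evaluation period".

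Section 14.5 gives the rule for the primary: "The lower bound of the 95% confidence interval will be compared to 1". This interval is not adjusted. The odds ratios by period "will be calculated with their corresponding adjusted 95% confidence intervals to test the secondary hypothesis #1".

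Section 14.6 covers the other two endpoints: "Overall quality of vision and overall comfort ratings will be analyzed separately using the same statistical method described in the primary analysis". It adds: "The hypothesis tests will be conducted using adjusted 95% confidence intervals of odds ratios". It does not say what the adjustment covers.

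Section 14.1 leaves further detail to a stand-alone SAP: "The SAP will be finalized prior to database lock". Section 14.8 schedules three descriptive interim summaries.

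**The concern.** A period adjustment run inside one endpoint's model controls error within that endpoint. It does nothing for the chance that some other endpoint gives a false positive. With three endpoints in separate models, an overall rate needs an order, a gate or a split of alpha between endpoints, and the supplied text has none.

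There are two smaller gaps:

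- Bright-light satisfaction is tested over one year at an unadjusted interval and again by period at adjusted intervals, with no gate between the two.
- It is unclear whether the one-year tests of hypotheses 2 and 3 are inside the adjustment. Section 14.4 names only periods, and Section 14.6 says only that the intervals are adjusted.

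A reader of Section 14.4 would take a superiority claim on quality of vision, comfort or a single period to be covered by an overall 5% guarantee that the described method does not give.

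**Working it through.** **The plan's own figure.** The formula in Section 14.2, with two-sided 0.05, 80% power and n = 3, reproduces 13 of the 15 cells of Table 4. For 0.70 against 0.80 at ρ = 0.7:

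N = (1.960·√0.375 + 0.8416·√0.37)² × 2.4 / (3 × 0.10²) = 234.5, printed as 234.

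The two cells that do not reproduce are in the 0.77/0.86 row: 145 and 242 are printed, and the formula gives 155.2 and 232.8. The largest recomputed cell is 234.5, so 240 completers per arm suffice for the primary test, and 240/0.80 = 300 enrolled.

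**Number of tests.** Three endpoints, each with one one-year test and three period tests, give 3 × (1 + 3) = 12 superiority tests.

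**Simple case.** Take only the three one-year tests, each on its own 95% interval. Each has a 2.5% chance of false superiority. If they are independent, the chance of at least one is 1 − 0.975³ = 7.3%.

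**All 12 tests.** Multivariate normal simulation under a global null.

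- Period correlation: 0.3, 0.5, 0.7 (the range in Table 4).
- Endpoint correlation: not in the documents, so assumed.
- One-year statistic: standardised mean of the three period statistics.
- Primary one-year critical value: 1.960.
- Period critical values, from the maximum over three periods: 2.376, 2.350, 2.298.
- With the one-year test in the same family: 2.411, 2.369, 2.306.

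Reading A puts the one-year tests of hypotheses 2 and 3 inside the adjustment. Reading B leaves them at plain 95% intervals. The table gives the chance of any false superiority claim; each range runs over the period correlations.

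| Assumed endpoint correlation | A | B |
|---|---|---|
| 0 | 8.0–8.5% | 9.3–10.9% |
| 0.3 | 7.5–8.1% | 8.7–10.2% |
| 0.5 | 6.9–7.5% | 8.0–9.4% |
| 0.7 | 6.0–6.6% | 6.9–8.2% |
| 0.9 | 4.6–5.2% | 5.4–6.3% |

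Over correlations 0–0.8 the ranges are 5.4–8.6% (A) and 6.2–11.0% (B); separate runs differ by about 0.1 point. Over the same settings, false superiority on quality or comfort alone is 3.9–5.0% (A) or 5.0–7.5% (B). On bright-light satisfaction alone, counting its one-year and period tests, it is 3.2–3.8%. The primary test alone stays at 2.5%.

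**Power cost of moving the one-year tests inside the adjustment.** Solve the Section 14.2 formula for power at 240 per arm, with c the critical value:

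Zβ = [√(240·3·(pT − pC)² / (1 + 2ρ)) − c·√(2·p̄·q̄)] / √(pC·qC + pT·qT)

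- 0.70/0.80, ρ = 0.7: c = 1.960 gives (1.732 − 1.200)/0.608, or 80.9%. c = 2.306 gives (1.732 − 1.412)/0.608, or 70.1%. The loss is 10.8 points.
- 0.65/0.77, ρ = 0.3: c = 1.960 gives (2.546 − 1.258)/0.636, or 97.9%. c = 2.411 gives (2.546 − 1.547)/0.636, or 94.2%. The loss is 3.7 points.

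These are the extremes over the 15 scenarios: 80.9–97.9% becomes 70.1–94.2%. The effect sizes are those for bright-light satisfaction and serve only as an illustration, because none are given for quality or comfort.

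**The case against.** **Each analysis at its own 5%.** Section 14.4 could be read as saying that each analysis is run at an overall 5%, with the period adjustment as the control inside it; Section 14.6 does analyse the endpoints separately. On that reading the wording is loose but nothing is contradicted. It strains a sentence that covers all planned analysis under one overall rate. If it is what the sponsor means, the restatement proposed here says so plainly.

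**The benchmark.** Section 14.4 says 5%, not 2.5%. Against a literal 5%, reading A keeps each part (bright light; quality or comfort) at or below 5%. Only the union exceeds it, and at an endpoint correlation of 0.9 even the union straddles 5%. This stands and limits the size of the finding.

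**The absent SAP.** The stand-alone SAP may add a hierarchy. That is possible, and the finding is confined to the supplied text. But the SAP need only be final before database lock, after interim summaries in an open-label study, so an order fixed that late would be less convincing.

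**Secondary endpoints in a registry.** Control across secondary endpoints in a non-randomised post-market study is a choice, and many plans openly decline it. That is fair, but this plan states an overall rate.

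**The numbering.** Secondary hypotheses are numbered 1 to 3, but nothing calls that a testing order.

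**Conclusion.** The sentence in Section 14.4 is wrong as written and should be corrected. The method described does not deliver an overall 5% rate across three endpoints. The chance of any false superiority claim is about 5.4–8.6% (A) or 6.2–11.0% (B), against the 2.5% that the interval rule implies in that direction. These figures assume a global null, period correlation 0.3–0.7 and endpoint correlation 0–0.8, the last of which the documents do not support with data. At 0.9, reading A gives about 4.6–5.2%, so the excess over a literal 5% would be small or nil.

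A reader might infer three stronger things that the documents do not support:

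- **That the primary conclusion is inflated or the study undersized.** There is one primary hypothesis with its own test at two-sided 5%, and 240 per arm is unaffected.
- **That the error reaches 10.9–16.6% (A) or 12.5–21.1% (B).** Those figures count false inferiority, which the plan never claims.
- **That a Bonferroni split across endpoints is required.** A fixed order also gives control.

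**What to change.** Choose one of the following before the first interim summary in Section 14.8.

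**Restate the claim.** Replace the wording in Section 14.4 with: *Two-sided 5% for the primary hypothesis. Secondary tests are adjusted within each endpoint across the evaluation periods and are not controlled across endpoints.* Also say whether the one-year tests of hypotheses 2 and 3 are inside that adjustment. The restatement alone costs no power. If those tests are now outside and are moved inside, their critical value rises from 1.96 to about 2.31–2.41, at a cost of about 4–11 points of power on the illustration above.

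**Keep the overall 5% claim.** Test the one-year odds ratios in a fixed order, primary first, each at two-sided 5%, stopping at the first failure. Place the period tests behind them, in one of two ways:

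- *A continued fixed order across endpoints.* If an endpoint's three period tests must all succeed before the next endpoint is opened, progress may be limited: for bright-light satisfaction all three succeed only about 26–56% of the time.
- *A 5%/3 split, with the period adjustment run within each endpoint.* The period critical value rises from 2.30–2.38 to 2.71–2.76. Before any gating, 12-month bright-light power falls from 56–73% to 41–58%. In a simulation of 2,250 effect and correlation patterns, the highest false-superiority rate with this split was 2.54%, which is 2.5% within simulation error.

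Neither way needs extra subjects, a joint model or a change to the primary test. The price is that a failure blocks every later claim. The primary passes about 81–98% of the time over Table 4's scenarios, but the blocking cost from quality and comfort cannot be computed from the documents.
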